8.6.4 Criteria for Discontinuing of Treatment with Study Drugs

Patients should discontinue treatment with either modakafusp alfa or pembrolizumab, or both, if they meet any of the criteria listed below. Patients who discontinue pembrolizumab for reasons other than irAEs may continue modakafusp alfa treatment as a single agent if modakafusp alfa discontinuation criteria are not met; patients who discontinue modakafusp alfa may continue pembrolizumab as a single agent if pembrolizumab discontinuation criteria are not met. In the event of discontinuation of study therapy (modakafusp alfa and pembrolizumab), patients will undergo the end of treatment (EOT) visit.

8.6.4.1 Criteria for Discontinuing Modakafusp Alfa

Study drug **must** be permanently discontinued if any of the following criteria are met:

1. Patient experiences an AE in Cycle 1 meeting criteria for a DLT that is considered life-threatening.
2. Confirmed progressive disease according to RECIST v1.1.
3. Start of new/subsequent anticancer treatment.
4. Confirmed pregnancy.
5. Patient meets any of the criteria for discontinuation specified in Section 8.10.

Study drug **may** be discontinued after discussion with the study sponsor, if any of the following criteria are met:

1. Any non-life-threatening AEs if the investigator determines that study continuation is no longer in the patient's best interest.
2. Any AE that changes the benefit-risk assessment for a patient.

3. Clinical deterioration of the patient as assessed by the investigator.
4. CR.
5. Unsatisfactory therapeutic response.
6. Study terminated by sponsor.
7. Withdrawal by subject.
8. Subject's death.
9. Lost to follow-up.
10. Delay of next cycle by more than 14 days.
11. Important protocol deviations from inclusion/exclusion criteria.

If treatment is discontinued, the EOT visit should be completed within 30 to 40 days after the last administration of modakafusp alfa.

8.6.4.2 *Criteria for Discontinuing Pembrolizumab*

Pembrolizumab will be discontinued if any of the criteria described in [Table 8.c](#) or the pembrolizumab SmPC have been met. Additionally, pembrolizumab may be discontinued for other reasons if it is considered in the best interest of the patient and discussed with the medical monitor.

Permanently discontinue pembrolizumab for any of the following:

- Any life-threatening adverse reaction (excluding endocrinopathies controlled with hormone replacement therapy).
- Grade 3 or 4 pneumonitis or recurrent pneumonitis of Grade 2 severity.
- Grade 3 or 4 nephritis.
- Grade 4 severe skin reactions or confirmed Stevens-Johnson syndrome or toxic epidermal necrolysis.
- AST or ALT greater than $5 \times \text{ULN}$ or total bilirubin greater than $3 \times \text{ULN}$.
 - For patients with liver metastases who begin treatment with Grade 2 AST or ALT, if AST or ALT increases by greater than or equal to 50% relative to baseline and lasts for at least 1 week.
- Grade 3 or 4 IRRs.
- Inability to reduce corticosteroid dose to 10 mg or less of prednisone or equivalent per day within 12 weeks of an irAE.
- Persistent Grade 2 or 3 adverse reactions (excluding endocrinopathies controlled with hormone replacement therapy) that do not recover to Grade ≤ 1 within 12 weeks after last dose of pembrolizumab.

- Any severe or Grade 3 treatment-related AE that recurs.

8.7 Excluded Concomitant Medications and Procedures

The following medications and procedures are prohibited during the study:

- Radical radiation or extended field radiation therapy for disease under study. Local radiotherapy for localized painful metastases or at risk of producing complications is permitted after agreement with the sponsor's medical monitor.
- Any other anticancer treatment or investigational agent other than modakafusp alfa, including agents that are commercially available for indications other than the disease under study that are being investigated for the treatment of the disease under study.
- Concomitant chronic corticosteroid administration of >20 mg/day of prednisone or equivalent unless given as premedication prior to administration of modakafusp alfa to prevent onset and severity of IRRs, as premedication prior to administration of certain blood products or for exacerbations of respiratory tract disorders, acute pain management, suspected or confirmed immune-mediated thrombocytopenia, immune-related AEs, or if tumor flare is suspected.

8.8 Permitted Concomitant Medications and Procedures

8.8.1 Premedication

Due to the occurrence of Grade 2 IRRs in 8 of 17 patients receiving modakafusp alfa at doses of 0.1 to 1.5 mg/kg Q3W in the current study as of the data cutoff of 23 January 2021, the following list of medications are mandatory in all cycles before infusion of modakafusp alfa to prevent and/or mitigate this potential AE.

1. Corticosteroid IV or orally (PO) (dexamethasone 10 mg to 20 mg or equivalent) 60 minutes to 2 hours before treatment.
2. Acetaminophen 650 mg to 1000 mg PO 60 minutes to 2 hours before treatment.
3. Diphenhydramine or equivalent 25 mg to 50 mg PO approximately 1 hour before treatment.

Montelukast may be given to patients who are intolerant to diphenhydramine or for whom diphenhydramine is ineffective. Additional premedications of nonsteroidal anti-inflammatory drugs (NSAIDs) and H₂ blockers could be added per investigator's discretion.

Medication(s) shall be administered according to medical standards and at sufficient time prior to start of infusion of modakafusp alfa that allows the premedication drugs to exert their effects.

For the phase 2 expansion phase, the history of IRR to prior CPI treatment will be collected.

During the infusion and for 6 hours post-infusion in the first 2 treatment cycles, patients should be continually monitored by medically qualified staff with access to emergency medical equipment and medications to manage IRRs. In Cycle 3 and beyond, patients should be continually monitored for at least 2 hours post the end of infusion, and the monitoring duration could be extended per a

patient's prior dosing experience. Potential IRRs shall be managed as medically indicated including, but not limited to, repeated administration of drugs described above.

For details about treatment of IRRs, please refer to Section 8.10.1. Procedures for reporting AESIs are described in Section 10.2.1.

8.8.2 Postinfusion Medication

Patients may receive concomitant medications on the first and second days after all infusions per institutional protocols.

8.8.3 Other Permitted Concomitant Medications and Procedures

All necessary supportive care consistent with optimal patient care will be available to patients as medically indicated. All blood products and concomitant medications will be recorded in the electronic case report forms (eCRFs, which refers to any media used to collect study data whether paper or electronic) as specified in the SOE (Appendix A).

The use of G-CSF and/or platelet transfusions is prohibited during the DLT evaluation period of the escalation phase (Cycle 1) unless deemed medically indicated by the investigator.

The following medications and procedures are permitted while the patient is receiving the study drug:

- Myeloid growth factors (eg, G-CSF, granulocyte macrophage-colony stimulating factor) and erythropoietin are permitted. Their general use should follow the product label, published guidelines, and institutional practice. [REDACTED]
- Patients should be transfused with RBCs and platelets as clinically indicated. Transfusions must be recorded in the concomitant procedure pages of the eCRF.
- Concomitant treatment with bisphosphonates will be encouraged for all patients with evidence of lytic destruction of bone or with osteopenia, according to the American Society of Clinical Oncology Clinical Practice Guidelines or institutional practice in accordance with the product label, unless specifically contraindicated. If bisphosphonate therapy was not started before the study start, it should be initiated as soon as clinically indicated.
- Topical or inhaled steroids (eg, for the treatment of asthma) are permitted.
- Systemic steroids for acute management of pain, suspected or confirmed immune-mediated thrombocytopenia or other disease or treatment-related complications are permitted.
- Intravenous immunoglobulins (IVIg) usage is acceptable for prolonged Grade 4 transfusion-dependent thrombocytopenia or other investigator criteria if it is considered that there is an underlying autoimmune mechanism.

- Thrombopoietin agonists are allowed for thrombocytopenia management at investigator's discretion.
- Vaccinations to prevent COVID-19 viral infections and other infections (eg, influenza, pneumococcus) are allowed at the investigator's discretion with the following considerations:
 1. Live vaccines are not recommended.
 2. Vaccination and modakafusp alfa dosing on the same day is not recommended.
 3. For patients in the dose escalation, vaccination in the Cycle 1 DLT evaluation period is not recommended.

Supportive measures consistent with optimal patient care may be given throughout the study.

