8.2 Definitions of Dose-Limiting Toxicities

Toxicity will be evaluated according to the NCI CTCAE v 5. A DLT is defined as any of the following AEs that occur in the escalation phase or in the combination safety lead-in phase during Cycle 1 unless they are considered by the investigator to be clearly unrelated to therapy with modakafusp alfa.

- Any Grade 5 TEAE.
- Febrile neutropenia: Grade ≥ 3 neutropenia ($ANC < 1.0 \times 10^9/L$) with fever and/or infection, where fever is defined as a single temperature $> 38.3^\circ C$ or sustained temperature of $\geq 38^\circ C$ for more than 1 hour.
- Grade 4 neutropenia lasting > 7 days.
- Grade 4 thrombocytopenia lasting more than 7 consecutive days, or if platelet transfusion is required, or if Grade ≥ 2 bleeding happens at any moment. A platelet count $< 10 \times 10^9/L$ at any time is a DLT.

- Grade ≥ 3 thrombocytopenia lasting longer than 14 days or accompanied by Grade ≥ 2 bleeding.
- **Any Grade 3 immune-related AEs such as pericarditis, pneumonitis, cardiotoxicity, hepatitis, or neurotoxicity.**
- Delay in the initiation of Cycle 2 by more than 14 days from the calculated start date due to a lack of adequate recovery of treatment-related hematological or nonhematologic toxicities.
- Any Grade ≥ 3 nonhematologic toxicity **with the following exceptions:**
 - Grade 3 arthralgia/myalgia that responds to nonsteroidal anti-inflammatory drugs (NSAIDs) within 1 week.
 - Grade 3 fatigue that lasts < 3 days.
 - Grade 3 endocrine disorder that is managed with or without therapy and the patient is asymptomatic.
 - Grade 3 or 4 inflammatory reaction attributed to a local antitumor response.
 - Grade 3 or 4 asymptomatic laboratory changes (other than renal and hepatic laboratory values) that can be successfully corrected (reversion of Grade 4 events to Grade ≤ 2 , reversion of Grade 3 events to Grade ≤ 1 or baseline) within 72 hours.
 - Isolated Grade 3 elevation of ALT and/or AST that resolves to Grade ≤ 1 or baseline within 7 days.
 - Grade 3 nausea and/or emesis that can be controlled to Grade < 3 in ≤ 3 days with the use of optimal antiemetics (defined as an antiemetic regimen that employs both a 5-hydroxytryptamine 3 serotonin receptor antagonist and a corticosteroid given in standard doses and according to standard schedules).
 - Grade 3 rash and pruritis that respond to a standard treatment and resolve or improve to Grade < 3 within 7 days.

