8.4 Phase 2 Modakafusp Alfa Dose Expansion

A minimum of 3 patients will be enrolled at the modakafusp alfa RP2D in combination with pembrolizumab 400 mg Q6W to evaluate safety and tolerability in a single safety lead-in phase. The safety lead-in phase will start with the enrollment of 3 initial patients to evaluate the tolerability during the Cycle 1 DLT evaluation period of modakafusp alfa with pembrolizumab. If there are no DLTs in the first 3 patients during Cycle 1 of the safety lead-in period with modakafusp alfa SA RP2D in combination with pembrolizumab 400 mg Q6W, the combination dose and regimen could be selected for the 3 melanoma disease cohorts.

If there is 1 DLT in the initial 3 patients in the safety-lead in period, an additional 3 patients will be enrolled at the same modakafusp alfa RP2D in combination with pembrolizumab 400 mg Q6W. If there are ≥ 2 DLTs in the first 3 patients at the modakafusp alfa SA RP2D, enrollment will resume at the next lower dose level of modakafusp alfa RP2D in combination with pembrolizumab. Other approved pembrolizumab dosing regimens (ie, 200 mg Q3W) could be tested in the safety-lead in period if 400 mg Q6W in combination with modakafusp alfa at one dose lower than RP2D is intolerable. For the safety lead-in period, patient enrollment will be staggered between the first and second patients by 7 days in the first dose cohort. The second and third patients can be dosed concurrently if the first patient in the cohort has gone through the Day 8 visit without clinically significant acute toxicities. Subsequent cohorts, if any, will not require staggering between patients.

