8.6.3.1 Modakafusp Alfa Dose Modification Guidelines

[Table 8.b](#) provides general dose modification recommendations for modakafusp alfa. When the dose of modakafusp alfa is withheld on the basis of these criteria, clinical and laboratory re-evaluation should be repeated at least weekly or more frequently, depending on the nature of the toxicity observed, until the toxicity resolves to Grade ≤ 1 or baseline. If there are transient laboratory abnormalities that, based on investigator assessment, are not clinically significant, continuation of therapy without dose modification is permissible upon discussion with the sponsor. See details for managing specific AEs in [Section 8.10](#).

Table 8.b Dose Modification Recommendations for Toxicities Possibly Related to Modakafusp Alfa

Criteria	Action
Grade 1 AEs	No dose reductions or interruptions.
Grade 2 AEs	Patients experiencing Grade 2 AEs considered related to study treatment that are not easily managed or corrected and are not tolerable to the patient, or AEs that are not acceptable in the investigator's judgment, should have study treatment interrupted until the AE resolves to Grade ≤ 1 or baseline and then restarted at the same dose or, depending on the toxicity, at the previous safe dose level or below.
Grade 3, Grade 4 (not life-threatening per seriousness criteria), and Grade 4 asymptomatic laboratory AEs	Hold modakafusp alfa until resolution to Grade ≤ 1 or baseline, and then resume treatment at a reduced dose level. In case of Grade 3 hematological toxicity (anemia, thrombocytopenia, neutropenia, or lymphopenia) or Grade 3 asymptomatic laboratory AEs, the patient can continue at the same dose or a reduced dose at the investigator's discretion.
Grade 4 (life-threatening per seriousness criteria) AEs	Permanently withdraw the patient from the study.
AEs of all grades	If treatment has been held for >14 consecutive days without resolution of the toxicity (to baseline or Grade ≤ 1), consider permanently discontinuing study treatment unless there is clinical benefit for the patient as assessed by the investigator and with sponsor's approval. Treatment can be resumed at a reduced dose level after resolution of AEs to Grade ≤ 1 or baseline.

AE: adverse event.

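### The visible Cycle 1 limit on G-CSF and platelet transfusion names only dose escalation, although the same DLT list also governs the 3-patient safety lead-in

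*Protocol*

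**What the plan says.** Protocol 8.2 defines a DLT as "any of the following AEs that occur in the escalation phase or in the combination safety lead-in phase during Cycle 1", unless the investigator considers the event clearly unrelated to modakafusp alfa. The list is the same for both settings. One item is "Grade 4 neutropenia lasting" more than 7 days. Another is "Grade 4 thrombocytopenia lasting more than 7 consecutive days, or if platelet transfusion is required".

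Protocol 8.8.3 restricts support in Cycle 1 and reads "G-CSF and/or platelet transfusions is prohibited during the DLT evaluation period of the escalation phase (Cycle 1) unless deemed medically indicated by the investigator". Its list of permitted medications, further down, allows myeloid growth factors and adds: "Their general use should follow the product label, published guidelines, and institutional practice". A redacted run comes directly after that sentence.

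Protocol 8.4 sets the lead-in action by the count in the first 3 patients. With no DLT, the combination dose could be selected for the three melanoma cohorts, each of up to 25 patients. "If there is 1 DLT in the initial 3 patients in the safety-lead in period, an additional 3 patients will be enrolled" at the same dose. With 2 or more, enrollment resumes at the next lower modakafusp alfa dose.

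SAP 7.3 counts a lead-in patient as DLT-evaluable after all Cycle 1 doses or after a Cycle 1 DLT. G-CSF use does not enter the definition.

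**The concern.** A criterion based on duration can be changed by treatment that shortens the event. For escalation, the protocol guards against this by keeping G-CSF out of the DLT window unless it is medically indicated. For the lead-in, which is scored on the same criteria, no visible sentence does so.

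The lead-in is also where one patient's score carries most weight. Three patients can open three cohorts. Protocol 4.3.5 says that no combination toxicology was done and presents the lead-in as the step that limits patient risk. Protocol 11.0 provides for no external data safety monitoring committee. Any distortion from discretionary support goes one way, towards fewer counted DLTs.

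**Working it through.** No figure in the plan is challenged, so the check sets the provisions side by side and then follows one patient through the decision rule.

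**1. Routes by which neutropenia becomes a DLT (Protocol 8.2).**
- Grade 3 or higher with fever and/or infection.
- Grade 4 for more than 7 days.
- Lack of recovery that delays Cycle 2 by more than 14 days.

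A patient without fever or infection, whose Grade 4 count recovers within 7 days on G-CSF and whose Cycle 2 is not delayed beyond 14 days, meets none of these. Protocol 8.6.2 accepts G-CSF to reach the neutrophil level needed for the next cycle, so the delay criterion does not catch this patient either.

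**2. Platelets compared with neutrophils.** A required platelet transfusion in Grade 4 thrombocytopenia is itself a DLT, so support is scored there. The list has no counterpart for G-CSF. The platelet criterion that still depends on duration is Grade 3 or higher for longer than 14 days, and 8.10.2 bases treatment decisions on counts taken before transfusion. The gap is therefore mainly about neutrophils.

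**3. How duration is observed.** Table 16.d schedules Cycle 1 hematology on Days 8 and 15, each with a window of 2 days either way. The two counts fall on Days 6 to 10 and 13 to 17, so they are between 13 − 10 = 3 and 17 − 6 = 11 days apart. When a dose is withheld, 8.6.3.1 says that "clinical and laboratory re-evaluation should be repeated at least weekly or more frequently". Unless extra counts are drawn, one follow-up count can decide whether an episode passed 7 days.

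**4. Effect on the lead-in rule (Protocol 8.4).** Take one patient whose Grade 4 neutropenia would have exceeded 7 days without G-CSF but is scored DLT-free.

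| DLTs in the other two | Count as scored | Action | Count with this patient as a DLT | Action |
|---|---|---|---|---|
| 0 | 0 | dose could be selected | 1 | add 3 patients |
| 1 | 1 | add 3 patients | 2 | next lower dose |
| 2 | 2 | next lower dose | 3 | next lower dose |

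The action changes in the first two rows. This is a property of any rule with cut-offs at 0, 1 and 2 of 3; it says nothing about how often such a patient occurs.

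**5. Frequency.** The only anchor is Protocol 4.3.3: neutropenia in 3 of 17 single-agent patients, all Grade 3 or higher and drug-related. 3/17 = 17.6%, as stated, with an exact 95% CI of 3.8% to 43.4%. The share at Grade 4, its duration, its cycle and the use of G-CSF are not given, and the patients did not receive the combination. No rate for the patient in step 4 can be derived from this.

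**6. What remains visible.**
- Protocol 10.1.2 makes a laboratory value that leads to therapeutic intervention an AE.
- For Grade 4 events that are not life-threatening, Table 8.b holds the drug until recovery, "and then resume treatment at a reduced dose level".
- TEAEs leading to dose modification are a primary endpoint of the lead-in (Protocol 5.2.1).
- SAP 7.12.2 provides individual neutrophil profiles by dose level. SAP 7.7 and Appendix A provide by-patient medication, laboratory and DLT listings.
- Protocol 6.1.2 places a safety data review between lead-in and expansion.

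**The case against.** Five points can be made on the other side.

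- *Redaction.* The hidden run may contain a growth-factor limit. This stands: a reader might infer that the plan has no lead-in restriction at all, and the documents do not support that. The run follows the general permission, however, not the prohibition, and the prohibition's own wording is visible and names only escalation.
- *The medical exception.* A patient treated for Grade 4 neutropenia is the obvious case for it, so the same thing can happen in escalation, and naming the lead-in would not stop it. This stands. The wording change reaches only discretionary or prophylactic use, which is why the fix has a second part.
- *The endpoint.* The DLT is an episode that actually lasts more than 7 days, and scoring tolerability under accepted supportive care is a legitimate choice. That is fair, and the untreated duration cannot be observed. But the protocol chose to restrict support in the escalation window, and no visible text explains why the lead-in should differ.
- *Existing outputs.* With 3 to 9 patients, the profiles and listings identify anyone affected. This largely stands, and a reader who infers that such events are hidden would be wrong. The outputs are, however, specified for SAP reporting, not for the dose decision.
- *Discretion.* With no DLTs the dose only could be selected, after safety review. This stands and keeps the effect small.

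The omission looks like escalation wording that was not carried forward. The vaccination advice in 8.8.3 and the replacement rule in 9.5 also name only escalation, and the protocol history shows the lead-in being added in Amendment 3, after Amendment 2 had clarified Cycle 1 medications for escalation. This is inference; no visible text states the reason.

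**Conclusion.** The mismatch is real on the visible text: one DLT list for two settings, and a limit on support in only one. Discretionary G-CSF in the lead-in could shorten a duration-based cytopenia and move the 3-patient count towards tolerable. The size cannot be quantified and is probably small, because the event is recorded, prompts dose action and is open to safety review before expansion.

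The conclusion assumes that the redacted run does not already extend the limit to the lead-in, and that G-CSF can shorten Grade 4 neutropenia. It does not say that every patient given G-CSF would have had a DLT, that G-CSF before Cycle 2 is improper, or that the lead-in will select a wrong dose at any particular rate. The documents support none of those readings. This is a cheap improvement to consider.

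**What to change.** Two changes:

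1. In Protocol 8.8.3, add *and the phase 2 safety lead-in* after the mention of the escalation phase, so that the Cycle 1 limit on G-CSF and platelet transfusion covers both DLT windows. Keep the medical exception.
2. At the lead-in dose-decision review, identify any patient given G-CSF for Grade 4 neutropenia in Cycle 1, and show the DLT count a second time with that patient also scored as a DLT. The as-scored count remains the governing rule.

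The lead-in action comes from the 3-patient rule, so the BLRM needs no second run.

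The cost is one phrase in the protocol and one extra line at a review that is already planned. Concomitant medication is already recorded in the eCRF, and no needed treatment is withheld. The downside is that some episodes that would have resolved within 7 days anyway will appear as DLTs in the sensitivity count, so the decision may be slightly more conservative.
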